Human Investigation Committee Signature

This protocol is valid through

SECTION V: RESEARCH PLAN**1. Statement of Purpose:** State the scientific aim(s) of the study, or the hypotheses to be tested.

The goal of this project is to address a major challenge in health disparities as defined by NIH and the Institute of Medicine, specifically, the need for accessible, effective, evidence-based treatments for Latino/as.

Specific aims are as follows:

- To adapt our existing CBT4CBT program for use with Spanish-speaking alcohol users in a web-based platform
- To conduct an 8-week randomized trial evaluating the feasibility and efficacy of adding CBT4CBT-Spanish to treatment as usual in a community based treatment program in a population of 90 Spanish-speaking individuals who meet current criteria for alcohol use disorder
- To evaluate the long-term durability and/or delayed emergence of treatment effects through a six month follow-up after termination of the study treatments. Given previous evidence regarding the durability of standard clinician-delivered CBT₄₁ and computer-assisted CBT4CBT₂₅, we hypothesize that CBT4CBTSpanish will be significantly more effective than standard treatment alone through the follow-up.

2. Background: Describe the background information that led to the plan for this project.

Provide references to support the expectation of obtaining useful scientific data.

A Health disparities among Latinos, accessibility of evidence based therapies (EBTs).

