Outlined below is the general strategy for data analyses for the randomized clinical trial in Phase 2 (years 3-5) of the study which will address each specific aim: (1) determination of the efficacy of treatments, and (2) analysis of the follow-up data, as well as our exploratory, secondary aims (analysis of mediators).

Outlined below is the general analytic strategy for addressing the specific aims for this Stage 1 trial:

1. Determination of Treatment Outcomes

a. *Data reduction*: Primary outcome variables have been defined *a priori* to reduce the risk of Type I error. Preparatory analyses include evaluation of baseline equivalence of treatment groups on demographic and prognostic variables and comparability of rates of data availability across conditions.

b. *Strategies for management of differential attrition*: Data analyses will be conducted on the intent-to-treat sample and we will attempt to follow all participants regardless of their retention in treatment. We have established our ability to contact and follow participants who drop out of treatment and to conduct true intent-to-treat analyses^{16, 208, 209}, including supplemental analyses that account for whether data was collected before or after dropout/withdrawal²⁰⁸. While we anticipate that assertive efforts to locate and interview participants who drop out of treatment will result in low numbers of missing participants and minimal missing data in the final dataset, we will minimize the impact of missing data through the use of random effects regression modelling²⁵¹⁻²⁵³.

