c. *Evaluation of treatment effects at posttreatment and follow-up*: The principal strategy for assessing the efficacy of the study treatments on outcome over time will be random effects regression models for continuously measured primary (e.g. percent days of abstinence by week) and secondary (e.g., acquisition of coping skills) outcome variables. The focus of the repeated measures analyses will be the 'contrast by time effects', which essentially evaluates whether the slopes, or rates of change, of one group differ from the slopes of another group. We have used these methods to evaluate main and interaction effects, with appropriate covariates (e.g., retention, compliance with treatment, time spent working with the CBT4CBT program) in multiple previous trials^{14, 151, 160, 200, 201, 254}. Follow-up data will be analyzed using random-effects regression modeling²⁵⁵ for our primary outcome measures across time, using the contrasts described above, with appropriate covariates (e.g., length of time in treatment, exposure to other treatment during follow-up). Random effects regression models have several advantages in follow-up data from clinical trials of substance users where participants are unlikely to attend follow-up evaluations precisely at the desired fixed points, and are less vulnerable than traditional MANOVA approaches to missing data^{208, 209, 251, 252}. As in our previous trials^{16, 126}, we estimate that our extensive efforts to track participants will yield a 90% follow-up rate.

d. *Adequacy of sample size*: This Stage 1 trial is intended to provide initial pilot testing and feasibility testing of the web-based CBT4CBT program in a Spanish-speaking sample of individuals with alcohol use disorder. Based on SSize software, the proposed sample sizes will enable us to detect effect sizes of .35 or higher for either hypothesis, which will be the criterion for determining whether CBT4CBT-Spanish-Alcohol has adequate promise to justify a fully powered randomized trial²⁵⁶. This sample size was sufficient for the English-language trials of the drug and alcohol versions of CBT4CBT, which yielded effect sizes of .46-.59^{13, 15, 16}.

Power calculations for random effects regression	Power	Estimated effect size	Estimated ICC	# of datapoints	Sample size per cell
H1: (CBt4CBT-S + ST) v ST, main effect for active treatment phase (assessed weekly, baseline-8weeks)	.80	.35	.40	9	45

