H2: (CBT4CBT-S + ST) vs ST, main effect for follow-up (assessed monthly, end of treatment-6 months)	.80	.50	.80	7	40

2. Treatment specificity and mediators

We will explore the extent to which participants improve coping skills over time using the ARRT as described above and the extent to which acquisition of coping skills may mediate outcome for CBT4CBT-Spanish-Alcohol in this sample. We have described our use of these models and strategies to evaluate treatment mediators in Preliminary Studies, above, and in several papers^{13, 105, 108, 151}. Following the general analytic framework outlined by Kraemer²⁵⁷, we will use the product of the coefficients method to evaluate the relationship between the mediator (e.g., acquisition of CBT-specific coping skills as measured by the ARRT), or indirect effect, and outcome^{155, 156, 258}. After running a regression equation to determine (1) the effect of treatment on the mediator (provides beta weight for a), we will evaluate (2) the strength of the relationship between the mediator, treatment, and outcome (provides beta b). Using MacKinnon's software PRODCLIN²⁵⁹, we will evaluate the asymmetric confidence intervals for the product of the regression estimates (a^*b).

SECTION VI: RESEARCH INVOLVING DRUGS, BIOLOGICS, PLACEBOS AND DEVICES

If this section (or one of its parts, A or B) is not applicable, state N/A and delete the rest of the section.

N/A

SECTION VII: HUMAN SUBJECTS

1. Subject Population:

Provide a detailed description of the types of human subjects who will be recruited into this study.

Participants will be individuals seeking outpatient treatment for alcohol use at the Connecticut Mental Health Center (CMHC), where the majority of clients are male (73%), middle aged (62%), unemployed (71%), unmarried (56%), and have not completed high school (64%). Spanish-speaking participants will be recruited from two CMHC outpatient programs (The Hispanic Clinic at [name] and the Substance Abuse Treatment Unit at [name]) or Connecticut Mental Health Center clinicians. Additionally, MAAS (The Multi- Cultural Ambulatory Addiction Service at [name]) has been appointed a recruitment site

2. Subject classification:

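### The power table gives no significance level or sidedness: at two-sided .05 its own inputs yield about .68 and .69 rather than .80, and .35 is not detectable with .80 power for H2 at two-sided or one-sided .05

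*Protocol*

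**What the plan says.** Protocol Section V.5, item 1.d (*Adequacy of sample size*), has a two-row table with columns for power, effect size, ICC, number of datapoints and sample size per cell.

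- The H1 row, for the treatment phase, is labelled "H1: (CBt4CBT-S + ST) v ST, main effect for active treatment phase (assessed weekly, baseline-8weeks", and its entries read "assessed weekly, baseline-8weeks) .80 .35 .40 9 45".
- The H2 row, for follow-up, reads "assessed monthly, end of treatment-6 months) .80 .50 .80 7 40".
- Both rows are labelled as main effects; H1 is the "main effect for active treatment phase".

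The text above the table attributes the calculation to SSize without giving its settings. It says the trial can detect effects of .35 and larger for H1 and H2 alike, and makes this the test of whether a fully powered trial is justified.

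On error rates, Section V.5 item 1.a and SAP item 1.a say only that primary outcomes were fixed in advance "to reduce the risk of Type I error". No level is given. Section V.1 words the follow-up aim directionally: "we hypothesize that CBT4CBTSpanish will be significantly more effective than standard treatment alone through the follow-up". Neither document declares a one-sided test.

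**The concern.** A power figure has no meaning without the significance level and sidedness behind it, and the plan supplies neither. A reader will assume two-sided .05, and on that assumption the printed .80 does not follow from the printed inputs.

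Two things are at stake. First, a reader would credit the trial with a 20% chance of missing the planned effect when the chance under ordinary two-sided testing is about 31 to 32%. Second, leaving sidedness open until analysis would allow it to be chosen after the data are seen, which could settle whether a borderline result counts as significant.

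The text also disagrees with its own table. It claims .35 for both hypotheses, while the H2 row is built on .50.

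**Working it through.** **Inputs, all from the power table.** H1: effect size d = .35, ICC = .40, m = 9 datapoints, n = 45 per cell. H2: d = .50, ICC = .80, m = 7, n = 40 per cell. Effects are standardised, so SD = 1. The 40 per cell in H2 fits the plan's 90% follow-up rate (45 × .9 = 40.5).

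**Formula.** For a group main effect over m equally correlated measurements, the variance of a person's mean is V = (1 + (m − 1) × ICC)/m. Then SE = √(2V/n) and z = d/SE. Power is Φ(z − 1.960) at two-sided .05 and Φ(z − 1.645) at one-sided .05. The effect detectable with .80 power is (1.960 + .842) × SE or (1.645 + .842) × SE.

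**Results.**

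- H1: V = (1 + 8 × .40)/9 = .4667; SE = √(2 × .4667/45) = .1440; z = .35/.1440 = 2.430.
- H2: V = (1 + 6 × .80)/7 = .8286; SE = √(2 × .8286/40) = .2035; z = .50/.2035 = 2.457.

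| | Printed | One-sided .05 | Two-sided .05 |
|---|---|---|---|
| H1 power at .35 | .80 | .784 | .681 |
| H2 power at .50 | .80 | .791 | .690 |
| H1 effect detectable with .80 power | .35 | .358 | .403 |
| H2 effect detectable with .80 power | .50 | .506 | .570 |
| H1 n per cell for .80 power | 45 | 48 | 60 |
| H2 n per cell for .80 power | 40 | 41 | 53 |

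A t rather than normal reference gives .671 and .680 at two-sided .05, so the approximation is not the cause.

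**Reproducing the printed .80.** One-sided .05 comes within two points in both rows but does not quite reach .80. Solving for the level that gives exactly .80: z − .842 = 1.589 for H1, a one-sided level of about .056; and 1.615 for H2, about .053.

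**Other structures at two-sided .05.** None gives .80 in both rows. For the next three lines, q = m − 1 post-baseline points and Vq = (1 + (q − 1) × ICC)/q. For the slope, S is the sum of squared deviations of time scaled 0 to 1, and d is taken as the difference at the last point.

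| Structure | Variance used | H1 power | H2 power |
|---|---|---|---|
| Baseline-adjusted mean | Vq − ICC² (.315; .193) | .84 | .999 |
| Change from baseline | Vq + 1 − 2 × ICC (.675; .233) | .52 | .996 |
| Linear slope | (1 − ICC)/S (.640; .257) | .55 | .99 |
| Mean under AR(1) correlation | average of the correlation matrix | .93 | .80 |

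AR(1) matches H2 alone. It misses H1 by a wide margin, and the table calls its parameter an ICC, which denotes exchangeable correlation.

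**H2 at .35.** z = .35/.2035 = 1.720. Power is Φ(1.720 − 1.960) = .41 two-sided and Φ(1.720 − 1.645) = .53 one-sided. Reaching .80 at .35 would take 107 or 84 per cell.

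**The case against.** The SSize settings are not visible, so any reconstruction depends on a model. A directional hypothesis also fits a one-sided calculation. On that view the defect is an omission in reporting and not a demonstrated arithmetic error. This stands in part. A reader might infer that the authors must have used a one-sided 5% test, or that the printed power is simply wrong. The documents support neither. One-sided .05 is the closest match among the variants tried, it falls slightly short of .80, and it is declared nowhere. The shortfall to .68 and .69 depends on two-sided .05 being the test used, and the plan does not say so either.

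A second objection is that this is a Stage 1 trial meant for pilot and feasibility testing, whose go-forward criterion is an effect size and not a p-value. At the effects cited from the English-language trials (.46 to .59), two-sided power for H1 is good: .46/.1440 = 3.19 gives .89, and .59/.1440 = 4.10 gives .98. This also stands, and it rules out the reading that the trial is too small for its purpose. It does not rescue the table, which attaches .80 to .35 and .50.

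Third, the analysis text in both documents focuses on the group-by-time contrast, while the table powers a main effect. Recomputed main-effect figures therefore do not describe the power of the slope comparison. That is correct and needs to be said beside the table.

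None of these objections touches the claim of .35 for both hypotheses, which conflicts with the H2 row without any assumption about the level.

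**Conclusion.** The point holds in a limited form. No significance level or sidedness is stated for H1 or H2. If the tests are two-sided at .05, power is about .68 for H1 at .35 and .69 for H2 at .50, some 11 to 12 points below the printed .80. The effects detectable with .80 power are then about .40 and .57, so the printed .35 and .50 are too small. If the tests are one-sided at .05, the table is nearly right, at about .78 and .79.

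These figures assume a main effect, exchangeable correlation at the printed ICC, complete data at the printed numbers per cell, and every listed datapoint used as an outcome.

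Under the same assumptions, the sentence claiming .35 for both hypotheses is wrong for H2 whichever sidedness is chosen.

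**What to change.** - Declare the significance level and sidedness for H1 and H2 in Protocol Section V.5 and in the SAP before analysis.
- If two-sided .05: restate the table for 45 and 40 per cell as H1 power .68 at .35 (detectable effect .40) and H2 power .69 at .50 (detectable effect .57).
- If one-sided .05 is intended: label the table so, use that test for the reported results of H1 and H2, and print .78 and .79.
- In either case, correct the sentence above the table so that it no longer claims .35 for H2.
- Add a note that the figures refer to the main effect named in the table and not to the difference in slopes that the analysis text emphasises.

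The cost is a few lines of text. Sample size and conduct are unchanged. The downside is that the stated figures become less favourable.

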We are proposing broad inclusion criteria that reflect the heterogeneity of individuals seeking treatment for alcohol use disorders in this setting. Literacy is not required for using the CBT4CBT program, and, as described below, most of the assessment instruments we use are clinical interviews or can be administered by reading the questions to the participants using procedures we have worked out in our ongoing and previous trials¹⁹³⁻¹⁹⁷. We are not requiring that participants have computer access for study inclusion, as participants can access the program at the clinic.

3. Procedures

a. Initial Screening

All new admissions will be invited to participate in the protocol within two weeks of their clinic appointment. They will be identified by their clinicians at CMHC, the Hispanic Clinic, SATU for MAAS, interest sheets, and clinic postings. Individuals who indicate they are interested in hearing more about the study will be offered a meeting with the research staff. An interest sheet providing a brief description of the study will be available for potential subjects to indicate their interest in learning more about the study and how to contact a member of the research team, should they be unable to speak with the research staff at the time of the clinic intake appointment. At the first interview, research staff will provide a brief overview of the protocol and obtain written informed consent. We use a multiple-choice test to assess participants' comprehension of the protocol^{122, 137}, with ample time to review questions to assure understanding of the protocol, consent, and treatments offered. After determination of eligibility, pretreatment assessments will be completed by the research assistant (see Table below).

b. Urn randomization

To prevent bias and increase the likelihood that treatment groups are balanced with respect to demographic variables (*gender, education*) and possible prognostic variables (severity of alcohol use, level of familiarity with and access to computers, level of acculturation) participants will be assigned to treatment conditions through urn randomization, using a Microsoft Access program that we have developed and implemented successfully in multiple previous trials¹⁹⁸⁻²⁰². In urn randomization, an algorithm modifies ongoing randomization probabilities based on prior

composition of treatment groups, maximizing multivariate equivalence of treatment groups²⁰³, while still retaining other benefits of random assignment²⁰⁴.

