### **1. Determination of Treatment Outcomes**

*a. Data reduction:* Primary outcome variables have been defined *a priori* to reduce the risk of Type I error. Preparatory analyses include evaluation of baseline equivalence of treatment groups on demographic and prognostic variables and comparability of rates of data availability across conditions.

*b. Strategies for management of differential attrition:* Data analyses will be conducted on the intent-to-treat sample and we will attempt to follow all participants regardless of their retention in treatment. We have established our ability to contact and follow participants who drop out of treatment and to conduct true intent-to-treat analyses, including supplemental analyses that account for whether data was collected before or after dropout/withdrawal. While we anticipate that assertive efforts to locate and interview participants who drop out of treatment will result in low numbers of missing participants and minimal missing data in the final dataset, we will minimize the impact of missing data through the use of random effects regression modelling.

*c. Evaluation of treatment effects at posttreatment and follow-up:* The principal strategy for assessing the efficacy of the study treatments on outcome over time will be random effects regression models for continuously measured primary (e.g. percent days of abstinence by week) and secondary (e.g., acquisition of coping skills) outcome variables. The focus of the repeated measures analyses will be the 'contrast by time effects', which essentially evaluates whether the slopes, or rates of change, of one group differ from the slopes of another group. We have used these methods to evaluate main and interaction effects, with appropriate covariates (e.g., retention, compliance with treatment, time spent working with the CBT4CBT program) in multiple previous trials. Follow-up data will be analyzed using random-effects regression modeling for our primary outcome measures across time, using the contrasts described above, with appropriate covariates (e.g., length of time in treatment, exposure to other treatment during follow-up). Random effects regression models have several advantages in

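### The H1 and H2 power rows size a main effect while the analysis text tests a slope difference, so the stated .80 and the .35 go-forward criterion are not defined on the contrast to be estimated

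*Protocol*

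**What the plan says.** **Power table (Protocol Section V, item 5, 1.d).** The H1 row is a "main effect for active treatment phase (assessed weekly, baseline-8weeks", with power .80, effect size .35, ICC .40, 9 datapoints and 45 per cell. Baseline is thus one of the nine points. The H2 row is also worded as a main effect, over the period from end of treatment to six months, with power .80, effect size .50, ICC .80, 7 datapoints and 40 per cell. The accompanying text applies .35 to both hypotheses and says of it: "which will be the criterion for determining whether CBT4CBT-Spanish-Alcohol has adequate promise to justify a fully powered randomized trial". Neither alpha nor sidedness is stated.

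**Analysis text (Protocol 1.c and SAP 1.c, same wording).** "The focus of the repeated measures analyses will be the 'contrast by time effects", a contrast "which essentially evaluates whether the slopes, or rates of change, of one group differ from the slopes of another group". Follow-up data are to be modelled "using the contrasts described above, with appropriate covariates (e.g., length of time in treatment, exposure to other treatment during follow-up".

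**Baseline and covariates.** SAP 1.a says "Preparatory analyses include evaluation of baseline equivalence of treatment groups on demographic and prognostic variables". The urn balances on gender, education and "possible prognostic variables (severity of alcohol use, level of familiarity with and access to computers, level of acculturation". The covariate examples that precede the follow-up sentence belong to an account of earlier trials ("We have used these methods to evaluate main and interaction effects, with appropriate covariates"). For H1 itself the plan names no covariate. The assessment table collects the Timeline Follow-Back at screening.

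**The concern.** A main effect is a difference in level averaged over visits. A group-by-time contrast is a difference in rate of change. They are different quantities with different standard errors, and they respond to different effect shapes. A power figure for one says nothing definite about the other.

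Three things are at stake:

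- The .80 claimed for H1 and H2 does not describe the analysis in 1.c.
- The protocol uses .35 as its promotion criterion, but a reader cannot tell whether .35 is an average gap, a gap at week 8 or something else. Two analysts could reach opposite go-forward decisions from the same data.
- The follow-up aim in Section V.1 covers both lasting effects and effects that emerge late. If the slope is the follow-up test, it addresses only the second.

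**Working it through.** **Inputs.** From the table: H1 d = .35, ICC = .40, m = 9, n = 45 per arm; H2 d = .50, ICC = .80, m = 7, n = 40. Assumed because not given: alpha .05, compound symmetry with unit variance per visit, no dropout, normal approximation. Power = Φ(effect/SE − z), with z = 1.960 two-sided or 1.645 one-sided.

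**Step 1: reproduce the rows as main effects.** The variance of a participant's mean is V = [1 + (m − 1)·ICC]/m, and SE = √(2V/n).

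- H1: V = (1 + 8 × .40)/9 = .467; SE = √(2 × .467/45) = .144; .35/.144 = 2.43. Power is .68 two-sided, .78 one-sided.
- H2: V = (1 + 6 × .80)/7 = .829; SE = √(2 × .829/40) = .204; .50/.204 = 2.46. Power is .69 two-sided, .79 one-sided.

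Both rows come close to .80 only one-sided. For H1 the matching n is 48 one-sided or 60 two-sided, against the stated 45.

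**Step 2: the H1 slope contrast.** With weeks 0 to 8, Σ(t − 4)² = 60, so the slope difference has SE = √[2 × (1 − .40)/60/45] = .0211 per week.

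- Constant gap of .35 from week 1, zero at baseline: nine-point average .35 × 8/9 = .311; least-squares slope .35 × 4/60 = .0233.
- Linear to .35 at week 8: average .175; slope .35/8 = .0438.
- Linear to .70 at week 8: average .35; slope .70/8 = .0875.

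| Shape of the effect | Main-effect power, two-sided (one-sided) | Slope power, two-sided (one-sided) |
|---|---|---|
| Constant .35 from week 1 | .58 (.70) | .20 (.30) |
| Linear, reaching .35 at week 8 | .23 (.33) | .55 (.67) |
| Linear, averaging .35 and reaching .70 | .68 (.78) | .99 (.99) |

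The slope test is the weaker of the two for the constant gap and the stronger for both linear shapes.

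**Step 3: could the row have been sized on a slope?** A line reaching .35 at week 8 needs 83 per arm (65 one-sided) for power .80. One averaging .35 needs 21 (17 one-sided). Neither gives 45.

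**Step 4: what 45 per arm detects on the slope.** Week-8 gap = 8 × (1.960 + .842) × .0211 = .47 SD two-sided (.42 one-sided).

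**Step 5: H2.** A gap of .50 that stays constant through follow-up has a slope difference of zero. The slope test then rejects only at the rate alpha, .05.

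**Step 6: baseline adjustment, if a mean contrast is used.** Weeks 1-8 as outcomes: V = (1 + 7 × .40)/8 = .475; SE = .145; unadjusted two-sided power for .35 is .67. Adjustment multiplies V by (1 − ρ²), where ρ is the correlation of baseline percent days abstinent with the participant's weeks 1-8 mean. At ρ = .2, .4 and .6, V = .456, .399 and .304, and power is .69, .75 and .85. The documents do not give ρ.

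**The case against.** **The mismatch need not mean low power.** This stands. A reader might infer that the slope test has less power than the row states. The documents do not support that, because the table gives no effect shape. Comparing a main effect that averages .35 with a line that only reaches .35 compares two different effects. Shape for shape, the slope test does better under both linear divergences.

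**Baseline is already used.** For a slope model this also stands: baseline is the time-0 outcome, so no extra covariate is needed. Adjustment matters only if a mean contrast is chosen. A reader might also infer that the plan excludes baseline adjustment, or that H1 will be adjusted for retention or program use. Neither follows. The covariate lists are open-ended, and the retention and compliance examples describe earlier trials.

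**A slope suits the follow-up aim.** In part. It is a direct test of delayed emergence, so it would be wrong to say that H2 cannot serve its aim. It does not serve the durability half. That a constant gap yields power equal to alpha is true by construction.

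**This is a Stage 1 trial, and .35 may be a threshold for the observed effect.** On that reading test power does not drive the decision. The threshold still has to be defined on an estimated quantity, and the protocol itself claims .80.

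**Conclusion.** The inconsistency is real and should be corrected. The power rows and the analysis text concern different contrasts for both hypotheses, so .80 is not the power of the described analysis and .35 has no stated meaning on a slope. The size of the problem is the spread: for H1, two-sided slope power runs from .20 to .99 according to what .35 is taken to mean, against .68 for a nine-point main effect averaging .35. The supportable conclusion is that the power of the planned contrast is undetermined, not that it is low.

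These figures rest on alpha .05, compound symmetry, no dropout and no variation between participants in slope. Such variation would lower the power of both contrasts, but the documents give no value for it. The closer one-sided match in Step 1 is an inference; the plan does not say that its tests are one-sided. Confidence is high that the texts conflict, and moderate on any particular power figure.

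**What to change.** 1. **Name one primary contrast for H1 and one for H2.** Define .35 (and .50 for H2) on it, and restate each power row with alpha, sidedness and the assumed effect shape. Enrolment need not change. If the slope stays for H1, the row would read: 45 per arm, ICC .40, power .80 for a week-8 gap of .47 SD (two-sided .05, no random slopes). For H2, a mean over follow-up matches the power row and the durability aim; report the slope as well for delayed emergence.

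2. **State how baseline is used.** For a mean contrast in H1, take weeks 1-8 as outcomes and baseline percent days abstinent, from the screening Timeline Follow-Back over a stated window, as covariate. For a slope contrast, keep baseline as the time-0 outcome; no further covariate is needed.

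Adjustment for the urn factors, and a constraint of equal arm means at baseline, are optional.

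**Cost.** SAP wording and two revised table rows; no new data or participants. Choosing a mean contrast changes the slope focus now stated in 1.c, and the SAP should say so openly. The gain from baseline adjustment may be small (.67 to .69 at ρ = .2), particularly if screening drinking predicts poorly in participants rescreened after detoxification.
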